EU	european union
Fc ϵ RI	IgE receptor
Fc ϵ RII	IgE receptor

FSH	Follicle Stimulating Hormone
GCP	Good Clinical Practice
GGT	Gamma-glutamyl transferase
β -hCG	Beta-Human Chorionic Gonadotropin
[REDACTED]	[REDACTED]
HRQoL	Health-Related Quality of Life
HSS	Hives Severity Score
HSS7	Weekly Hives Severity Score
IB	Investigator's Brochure
IC	Informed consent
ICF	Informed Consent Form
ICH	International Council for Harmonisation
IEC	Independent Ethics Committee
IgE	Immunoglobulin E
IN	Investigator Notification
INR	International Normalized Ratio
IRB	Institutional Review Board
IRT	Interactive Response Technology
ISS	Itch Severity Score
ISS7	Weekly Itch Severity Score
IUD	Intrauterine device
IUS	Intrauterine system
JDA	japanese dermatological association
LLOQ	lower limit of quantification
LTRA	Leukotriene Receptor Antagonist
MedDRA	Medical dictionary for regulatory activities
MMRM	Mixed effect Model Repeat Measurement
MoA	Mechanism of Action
MRI	Magnetic Resonance Imaging
NYHA	New York Heart Association
[REDACTED]	[REDACTED]
[REDACTED]	[REDACTED]
PMDA	Pharmaceuticals and Medical Devices Agency
PRO	Patient Reported Outcomes
PSD	Premature subject discontinuation
PT	prothrombin time
q4w	Every 4 weeks
QALYs	Quality-adjusted life-years
QMS	Quality Management System
QoL	Quality of life
QTcF	QT interval corrected by Fridericia's formula
SAE	Serious Adverse Event

sc	Subcutaneous
sCr	Serum creatinine
SD	standard deviation
SOC	System organ class
SOP	Standard Operating Procedure
SUSAR	Suspected Unexpected Serious Adverse Reactions
TBL	total bilirubin
TD	Study Treatment Discontinuation
UAS	Urticaria Activity Score
UAS7	Weekly Urticaria Activity Score
ULN	upper limit of normal
UPDD	Urticaria patient daily diary
VAS	Visual Analog Scale
[REDACTED]	[REDACTED]
WHO	World Health Organization
WoC	Withdrawal of consent
[REDACTED]	[REDACTED]

Glossary of terms

Additional treatment	Medicinal products that may be used during the clinical trial as described in the protocol, but not as an investigational medicinal product (e.g. any background therapy)
Assessment	A procedure used to generate data required by the study
Cohort	A specific group of subjects fulfilling certain criteria and generally treated at the same time
Control drug	A study drug (active or placebo) used as a comparator to reduce assessment bias, preserve blinding of investigational drug, assess internal study validity, and/or evaluate comparative effects of the investigational drug
Dosage	Dose of the study treatment given to the subject in a time unit (e.g. 100 mg once a day, 75 mg twice a day)
eCRF	Electronic case report form
Electronic Data Capture (EDC)	Electronic data capture (EDC) is the electronic acquisition of clinical study data using data collection systems, such as Web-based applications, interactive voice response systems and clinical laboratory interfaces. EDC includes the use of Electronic Case Report Forms (eCRFs) which are used to capture data transcribed from paper source forms used at the point of care
Enrollment	Point/time of subject entry into the study at which informed consent must be obtained (i.e. prior to starting any of the procedures described in the protocol)
eSource	eSource Direct Data Entry (DDE) refers to the capture of clinical study data electronically, at the point of care. eSource combines source documents and case report forms (eCRFs) into one application, allowing for the real time collection of clinical trial information to sponsors and other oversight authorities, as appropriate.
Investigational drug/treatment	The drug whose properties are being tested in the study
Other treatment	Treatment that may be needed/allowed during the conduct of the study (i.e. concomitant or rescue therapy)
Part	A sub-division of a study used to evaluate specific objectives or contain different populations. For example, one study could contain a single dose part and a multiple dose part, or a part in subjects with established disease and in those with newly-diagnosed disease
Patient	An individual with the condition of interest for the study
Period	The subdivisions of the trial design (e.g. Screening, Treatment, Follow-up) which are described in the Protocol. Periods define the study phases and will be used in clinical trial database setup and eventually in analysis
Premature subject withdrawal	Point/time when the subject exits from the study prior to the planned completion of all study drug administration and/or assessments; at this time all study drug administration is discontinued and no further assessments are planned
Personal Data	Subject information collected by the Investigator that is transferred to Novartis for the purpose of the clinical trial. This data includes subject identifier information, study information and biological samples
Screen Failure	A subject who did not meet one or more criteria that were required for participation in the study
Source Data/Document	Source data refers to the initial record, document, or primary location from where data comes. The data source can be a database, a dataset, a spreadsheet or even hard-coded data, such as paper or eSource

Start of the clinical trial	The start of the clinical trial is defined as the signature of the informed consent by the first subject
Study treatment	Any single drug or combination of drugs or intervention administered to the subject as part of the required study procedures
Study treatment discontinuation	When the subject permanently stops taking any of the study drug(s) prior to the defined study treatment completion date (if any) for any reason; may or may not also be the point/time of study discontinuation
Subject	A trial participant (can be a healthy volunteer or a patient)
Subject number	A unique number assigned to each subject upon signing the informed consent. This number is the definitive, unique identifier for the subject and should be used to identify the subject throughout the study for all data collected, sample labels, etc.
Treatment arm/group	A treatment arm/group defines the dose and regimen or the combination, and may consist of 1 or more cohorts
Variable	A measured value or assessed response that is determined from specific assessments and used in data analysis to evaluate the drug being tested in the study
Withdrawal of consent (WoC)	Withdrawal of consent from the study occurs only when a subject does not want to participate in the study any longer and does not allow any further collection of personal data

Amendment 01(14-Feb-2020)

Amendment rationale:

CQGE031C1301 is currently recruiting. This amendment primarily aims to provide clarification on:

- a. Clarifies that an urinalysis sample is to be collected Week 24
- b. Clarifies that if a subject takes concomitant omalizumab (outside of study assigned treatment), the subject must discontinue from the study, in which case, [REDACTED]/ADA samples should not be collected at the End of Study (EoS) visit.
- c. Clarifies that all subjects will be given three stool samples collection kits at screening Visit1 and Visit320.

It also includes other minor clarifications and editorial changes.

Changes to protocol and rationale:

- **Glossary of terms:** updated with the ‘Personal data’ definitions.
- **Protocol summary includes the following changes:**
 - “CSU diagnosis for \geq 6 months” changed to “CSU diagnosis for \geq 6 months (defined as onset of CSU with supporting documentation)”. Section 5.1 updated accordingly
 - “Subjects must be on H1-AH at only approved doses for treatment of CSU starting at Visit 1 (Day -28 to Day -14)” changed to “Subjects must be on H1-AH at only local label approved doses for treatment of CSU starting at Visit 1 (Day -28 to Day -14)” similar change is reflected in Section 4.1.1 and Section 5.1
 - “Any H2 antihistamine, Leukotriene Receptor Antagonist (LTRA) (montelukast or zafirlukast) or H1 antihistamines use at greater than approved dose after Visit 1” changed to “Any H2 antihistamine use or LTRA (montelukast or zafirlukast) after Visit 1 and any H1 antihistamine used as background medication at greater than local label approved doses after Visit 1” similar changes is reflected in Section 5.2
- **Section 4.1.1:** Added, “If a subject must switch to another background H1-AH (at approved dose) as a result of an AE, the subject will be considered to have remained on stable treatment.”
- **Section 5.1:** Included the word “local label” in Inclusion Criterion 4.
- **Section 5.2:** Added the term “background medication” and “local label” to Exclusion Criterion #10 in order to clarify that higher than approved doses of H1-AH as background medication are not allowed after Visit 1. This criterion does not apply to H1-AH taken as rescue medication which can be taken up to 4 times the approved dose.
- **Section 5.2:** Exclusion criterion 14 is amended to exclude hypersensitivity to all study drugs
- **Section 5.2:** Exclusion criterion 19, changed “History of” to “History of” and clarifies, that an INR > 1.5 (not INR > 1.5 ULN) is an exclusion criterion for this study.
- **Section 5.2:** Exclusion criterion 24, changed “basic contraception methods” to “Acceptable contraception methods” to be consistent with the CTFG guidelines for

contraception requirements in order to participate in the study. Section 4.5 and Section 7 updated accordingly.

- **Section 6.2.2: Table 6-2**

- Clarifies the term Routine as “more than 3 doses over a 5 day period” use of oral corticosteroids. Included IV/IM/IA corticosteroids as prohibited systemic routes of corticosteroid administration, with minimum required period without medication mentioned as 30 days prior to Visit 1.
- Included the phrase “Other immunosuppressive medication with or without known effect on CSU including but not limited to” to clarify that immunosuppressive medication is not limited to the medications mentioned in the table.
- Revised the footnote to clarify the use of oral corticosteroids as rescue therapy is allowed only after Week 12.
- Footnote clarifies that other preparations of corticosteroids (CS) with limited systemic exposure for non-CSU indications can be used (e.g. Intra nasal or any topical CS) as-needed basis

- **Section 6.2.2:** Section is updated to clarify that if subjects are administered omalizumab (outside of study assigned treatment) in the follow-up phase they should be discontinued from the study and collection of any efficacy or safety assessments should not be done at EoS visit. Table 8-1 footnotes updated accordingly. Section 9.1.1 updated accordingly
- **Section 6.2.3:** Provided clearer guidance and discontinuation criteria on the use of oral corticosteroids as rescue therapy and deleted the sentence indicating that instructions on use of corticosteroids will be provided to the investigators.

- **Section 8:** Following changes made to Table 8-1

- Clarification added to “Family history of malignancy” indicating that CRF is to be completed retrospectively for any subject who develops malignancy during the study.
- There is no need to dispense H1-AH or oral corticosteroids as rescue medications at Visit 1999 or Week 64, hence “s” deleted at that Visit
- Clarifies that “At Visit 1 and Visit 320, dispense 3 stool collection kits. Patients should collect samples, within seven days of Visit1 and in the week prior to Visit 1999/EOS/PSD”
- Added “INR at Visit 1, V110 and UPV” for determining exclusion criteria 19 and liver safety follow up. Table 8-10 updated accordingly.
- Added Urine Dipstick to Visit 170/Week 24 for renal safety monitoring
- Added a separate line for “serum β -hCG” to clarify that a serum β -hCG sample should be taken for all pre-menopausal women who are not surgically sterile at Visit 1, followed by urine pregnancy test starting at V110 to Visit 1999/EOS/PSD.

- **Section 8.4.1:** is updated with text ‘In case of lab abnormalities, an additional re-draw for central laboratory assessment is allowed during the screening period to confirm eligibility criteria’ and ‘A serum β -hCG will be collected for all pre-menopausal women who are not surgically sterile at Visit 1’.

- **Section 8.4.3:** Clarification is provided on stool sample dispensation and collection of stool samples at not only Screening period Visit 1 and Visit 320 but also advised that if diarrhea, or any other symptoms suggestive of parasitic infection, develops at any time

before the end of study. The section also clarifies that pathogenicity of parasitic organisms will be defined as per the local laboratory.

- **Section 8.4.4:** Section update to provide clear guidance on pregnancy and assessments of fertility
- **Section 10.1.3:** Section updated to provide clarification on SAE reporting
- **Section 10.1.4:** Clarifies that pregnancy follow-up should be for up to 12 months following the birth of the baby.
- **Section 11.2:** the updated details pertaining to 'Stool samples will be processed by local labs and the results will be collected by Novartis via eCRFs' AND Patients will fill in their daily diary data on a smart phone device at home. PROs will be completed by patients on site on the day of applicable visits.
- **Section 16.2:** Table 16-1 and 16-2 clarifies the definition of liver events to be identified based on Guidance for detection, assessment, and management of drug-induced liver injury (DILI) in clinical development, Version 2 (15-Apr-2019)
- **Section 16.3:** Updated Table 16-3 and 16-4 based on the Clinical Development Safety Guideline for Drug Induced Nephrotoxicity Version 2.0 (DIN ClinDevSafetyGuide 2017)
- **Section 16.6:** Updated Appendix 6: World allergy organization grading system based on Cox L, Sanchez-Borges M, Lockey RF (2017) World Allergy Organization Systemic Allergic Reaction Grading System: Is a Modification Needed?. J Allergy Clin Immunol Pract; 5(1):58-62. Reference in section 9.1.1 updated accordingly.

Protocol summary

Protocol number	CQGE031C1301
Full Title	A multi-center, open-label study to investigate the safety/tolerability and efficacy of ligelizumab (QGE031) in the treatment of adult Japanese patients with Chronic Spontaneous Urticaria (CSU) inadequately controlled with H1 antihistamines
Brief title	A Phase III study of safety and efficacy of ligelizumab in the treatment of CSU in Japanese patients inadequately controlled with H1- antihistamines
Sponsor and Clinical Phase	Novartis Phase III
Investigation type	Drug
Study type	Interventional
Purpose and rationale	The purpose of this study is to evaluate the safety and efficacy of ligelizumab in adult Japanese subjects with CSU, who remain symptomatic despite treatment with H1-antihistamines (AHs) at locally approved doses.
Primary Objective(s)	The primary objective of this study is to investigate the safety and tolerability of ligelizumab 120 mg subcutaneous (sc) every 4 weeks (q4w) for 12 months.
Secondary Objectives	The secondary objective is to evaluate the efficacy of ligelizumab 120 mg sc q4w by evaluation of: 
• Weekly Urticaria Activity Score (UAS7), Weekly Hives Severity Score (HSS7) and Weekly Itch Severity Score (ISS7) change from Baseline over time• Achievement of the complete UAS7 = 0, HSS7 = 0 and ISS7 = 0 response over time• Profile of change from baseline in the Dermatology Life Quality Index (DLQI)• Achievement of DLQI = 0/1 by visit up to end of study (EoS)
Study design	This is a Phase III multi-center, open-label, single arm study. There is screening period of up to 28 days, a 52 week treatment period, and a 12 week post-treatment follow-up period.
Population	The study population will consist of approximately 65 male and female subjects aged \geq 18 years who have been diagnosed with CSU and who remain symptomatic despite the use of H1-AH.
Key Inclusion criteria	
• Signed informed consent must be obtained prior to participation in the study• Male and female subjects \geq 18 years of age at the time of screening• CSU diagnosis for \geq 6 months (defined as onset of CSU with supporting documentation)• Diagnosis of CSU refractory to H1-AH at locally-approved doses at the time of Baseline (Visit 110, Day 1), as defined by all of the following:
• The presence of itch and hives for \geq 6 consecutive weeks at any time prior to Visit 1 (Day -28 to Day -14) despite current use of non-sedating H1-AH (at locally approved doses) during this time period• UAS7 score (range 0-42) \geq 16 and HSS7 (range 0-21) \geq 8 during the 7 days prior to baseline (Visit 110, Day 1)

	
Subjects must be on H1-AH at only local label approved doses for treatment of CSU for starting at Visit 1 (Day -28 to Day -14)Willing and able to complete a daily symptom electronic Diary (eDiary) for the duration of the study and adhere to the study visit schedulesSubjects must not have had any missing eDiary entries in the 7 days prior to baseline (Day 1, Visit 110). i.e., 14 eDiary entries required. Rescreening may be considered only once
Key Exclusion criteria	
History of hypersensitivity to any of the study treatments or excipients or to drugs of similar chemical classes (i.e. to murine, chimeric, or human antibodies)Subjects having a clearly defined, predominant trigger of their chronic urticaria (CU) (chronic inducible urticaria (CINDU)) including
urticaria factitia (symptomatic dermographism), cold-, heat-, solar-, pressure-, delayed pressure-, aquagenic-, cholinergic-, or contact- urticariaDiseases, other than chronic urticaria, with urticarial or angioedema symptoms such as urticarial vasculitis, erythema multiforme, cutaneous mastocytosis (urticaria pigmentosa), and hereditary or acquired angioedema (e.g., due to C1 inhibitor deficiency)Subjects with evidence of helminthic parasitic infection as evidenced by stools being positive for a pathogenic organism according to local guidelines. All subjects will be screened at Visit 1. If stool testing is positive for pathogenic organism, the subject will not enter treatment period and will not be allowed to rescreenAny other skin disease associated with chronic itching that might influence in the investigator's opinion the study evaluations and results (e.g. atopic dermatitis, bullous pemphigoid (BP), dermatitis herpetiformis, senile pruritus, etc)Prior exposure to ligelizumabAny H2 antihistamine use or LTRA (montelukast or zafirlukast) after Visit 1 and any H1 antihistamine used as background medication at greater than local label approved doses after Visit 1
Study treatment	Ligelizumab 120 mg sc q4w
Efficacy assessments	
Weekly urticaria activity score (UAS7)Weekly hives severity score (HSS7)Weekly itch severity score (ISS7)Dermatology Life Quality Index (DLQI)
Key safety assessments	Safety evaluations include adverse events (AEs), laboratory values, vital signs and electrocardiogram (ECG).
Other assessments	
132 [REDACTED]
 
• [REDACTED] Anti-drug antibodies (ADA), [REDACTED] 
132 [REDACTED]

Data analysis	As the study objective is to assess the safety with no specific safety hypothesis, treatment emergent adverse events during the study will be considered as a primary variable. All adverse events which start after the first dose of the study medication will be summarized as treatment emergent adverse event by system

	organ class (SOC) and preferred term. No formal statistical analysis will be provided.
Key words	Anti-Immunoglobulin E (IgE), chronic spontaneous urticaria (CSU), safety, Japanese, hives severity score (HSS), itch severity score (ISS), urticaria activity score (UAS), long term, ligelizumab, QGE031, UAS7

1 Introduction

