Ligelizumab (QGE031) is a humanized IgG-type monoclonal antibody that binds to human IgE with higher affinity than omalizumab. Upon binding to specific epitopes in the C3 region of IgE, ligelizumab is able to block the interaction of IgE with both the high and low affinity IgE receptors (Fc ϵ RI and Fc ϵ RII). Ligelizumab does not mediate IgE receptor cross-linking and consequent histamine release (i.e. is non-activating). This overall mechanism of action (MoA) is shared with omalizumab (Chang et al 2015).

When subjects are treated with ligelizumab, circulating IgE is rapidly bound by the anti-IgE antibody and becomes inaccessible to IgE receptors on mast cells and basophils (Arm et al 2014, Gauvreau et al 2016). Ligelizumab has demonstrated dose- and time-dependent suppression of free IgE, reduction in basophil Fc ϵ RI expression and thus basophil surface IgE, and inhibition of skin prick test responses to allergens, superior in extent and duration to those observed with omalizumab (Arm et al 2014, Gauvreau et al 2016). IgE is necessary for the enhanced expression of the Fc ϵ RI seen in atopic subjects (MacGlashan et al 1997, MacGlashan et al 1998), and thus a decrease in Fc ϵ RI expression on circulating basophils accompanies ligelizumab treatment. Other potentially beneficial effects from anti-IgE therapy include decreased IgE production (Lowe and Renard 2011), reduced IgE+ B cell numbers (Ota et al 2009) and reduced cytokine production by T cells (Coyle et al 1996).

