4.1 Rationale for study design

Data from the dose-range finding Study [[CQGE031C2201](#)] suggest that ligelizumab treatment improves itch and hives in adult subjects with CSU who have failed treatment with H1-antihistamines and those who failed treatment with a combination of H1 and H2 antihistamines and LTRA. The Phase III studies [[CQGE031C2302](#)] / [[CQGE031C2303](#)] are ongoing to further evaluate the efficacy and safety of ligelizumab in adults and adolescent CSU subject's refractory to antihistamines at ligelizumab doses 72 mg or 120 mg for 1 year, respectively. As the number of Japanese CSU patients exposed to ligelizumab of the intended dose or higher for registration is expected to be limited, the study, CQGE031C1301, is designed to obtain additional safety data of ligelizumab of 120 mg for one year in Japanese CSU patients to support the registration of ligelizumab in Japan.

An open-label design without comparator arm is considered adequate to evaluate long term safety for CSU in Japanese and accepted by Japanese Health Authority.

The target population for this study consists of CSU subjects who remain symptomatic despite treatment with H1-AHs at locally approved doses.

Subjects treated with omalizumab previously as well as subjects with chronic spontaneous urticaria as their predominant disease who also suffer from chronic inducible urticaria will be allowed to enroll into this study to collect the safety data in Japanese CSU patients.

After the completion of the treatment period, subjects will enter a post-treatment follow-up period to allow for further characterization of [REDACTED], collection of additional efficacy and safety data (eg, relapse), and evaluation of the presence of anti-drug antibodies (ADAs).

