5.2 Exclusion criteria

Main study

1. Use of other investigational biological drugs within 5 half-lives, or within 30 days (for small molecules) prior to Visit 1, or until the expected PD effect has returned to baseline (for biologics), whichever is longer.
2. History of hypersensitivity to any of the study treatments or excipients or to drugs of similar chemical classes (i.e. to murine, chimeric, or human antibodies).

3. Subjects having a clearly defined, predominant trigger of their chronic urticaria (chronic inducible urticaria) including:
 - urticaria factitia (symptomatic dermographism), cold-, heat-, solar-, pressure-, delayed pressure-, aquagenic-, cholinergic-, or contact-urticaria.
4. Diseases, other than chronic urticaria, with urticarial or angioedema symptoms such as urticarial vasculitis, erythema multiforme, cutaneous mastocytosis (urticaria pigmentosa), and hereditary or acquired angioedema (e.g., due to C1 inhibitor deficiency).
5. Subjects with evidence of helminthic parasitic infection as evidenced by stools being positive for a pathogenic organism according to local guidelines. All subjects will be screened at Visit 1(see [Section 8.4.3](#)). If stool testing is positive for pathogenic organism, the subject will not enter treatment period and will not be allowed to rescreen.
6. Any other skin disease associated with chronic itching that might influence in the investigator's opinion the study evaluations and results (e.g. atopic dermatitis, bullous pemphigoid, dermatitis herpetiformis, senile pruritus, etc.).
7. Prior exposure to ligelizumab.
8. Any H2 antihistamine use after Visit 1.
9. Any LTRA (montelukast or zafirlukast) after Visit 1.
10. Any H1 antihistamine used as background medication at greater than local label approved doses after Visit 1.
11. History or evidence of ongoing alcohol or drug abuse, within the last 6 months prior to baseline (Visit 110, Day 1).
12. Inability to comply with study and follow-up procedures.
13. Use of prohibited treatment detailed in protocol ([Table 6-2](#)).
14. Contraindications to or hypersensitivity to suggested rescue medications including but not limited to fexofenadine, loratadine cetirizine, rupatadine, epinephrine, levocetirizine, desloratadine or any of their ingredients.
15. Documented history of anaphylaxis.

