16. History of malignancy of any organ system within the past 5 years (except for basal cell carcinoma, actinic keratoses or Bowen disease (carcinoma in situ) that have been treated with no evidence of recurrence in the past 12 weeks; carcinoma in situ of the cervix or non-invasive malignant colon polyps that have been removed).
17. Presence of clinically significant cardiovascular (such as but not limited to myocardial infarction, unstable ischemic heart disease, New York Heart Association (NYHA) Class III/IV left ventricular failure, arrhythmia and uncontrolled hypertension within 12 months prior to Visit 1), neurological, psychiatric, metabolic, or other pathological conditions such as but not limited to cerebrovascular disease, neurodegenerative diseases, or other neurological disease, uncontrolled hypo- and hyperthyroidism and other autoimmune diseases, hypokalemia, hyperadrenergic state, or ophthalmologic disorder that could interfere with or compromise the safety of the subjects, interfere with evaluation or interpretation of the study results, or preclude completion of the study.
18. Medical examination or laboratory findings that suggest the possibility of decompensation of co-existing conditions for the duration of the study. Any items that are cause for uncertainty will be reviewed with the investigator.

19. History of, or current treatment for, hepatic disease including but not limited to acute or chronic hepatitis, cirrhosis or hepatic failure or Aspartate aminotransferase (AST)/Alanine aminotransferase (ALT) levels of more than 1.5 x upper limit of normal (ULN) and International Normalized Ratio (INR) of more than 1.5 at Visit 1.(see [Section 8.4.1](#))
20. History of renal disease or creatinine level above 1.5x ULN at Visit 1.
21. Platelets < 100,000/ μ L at Visit 1.
22. History of long QT syndrome or whose QT interval corrected by Fridericia's formula (QTcF) (Fridericia) measured at Visit 1 is prolonged (> 450 ms for males or > 460 ms for females) and confirmed by a central assessor (these subjects should not be re-screened).
23. Pregnant or nursing (lactating) women.
24. Women of child bearing potential, defined as all women physiologically capable of becoming pregnant, unless they are using basic (acceptable effective) methods of contraception for the duration of study (approx. 4 months, i.e. 5 half-lives, after last dose of ligelizumab). Acceptable contraception methods include:

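### Read literally, the hypersensitivity exclusion's list of related antibody classes leaves out humanized antibodies, the class the protocol gives ligelizumab

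*Protocol*

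**What the plan says.** Criterion 2 in Protocol section 5.2 excludes a history of hypersensitivity under three limbs: the study treatments, their excipients, and a related class of drugs. The third limb reads "or to drugs of similar chemical classes (i.e. to murine, chimeric, or human antibodies". The Key Exclusion criteria in the Protocol summary use the same wording: "to drugs of similar chemical classes (i.e. to murine, chimeric, or human antibodies".

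Protocol section 1.1 gives the study drug's class: "Ligelizumab (QGE031) is a humanized IgG-type monoclonal antibody that binds to human IgE with higher affinity than omalizumab".

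Four other criteria in section 5.2 bear on the point:

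- Criterion 7 excludes "Prior exposure to ligelizumab".
- Criterion 14 excludes "Contraindications to or hypersensitivity to suggested rescue medications".
- Criterion 15 excludes "Documented history of anaphylaxis".
- Criterion 17 excludes a range of pathological conditions "that could interfere with or compromise the safety of the subjects", among other grounds.

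**The concern.** The related-class limb is meant to identify drugs close enough to ligelizumab that a past reaction to one of them should keep a subject out. It does so with a definition, introduced by *i.e.*, that names murine, chimeric and human antibodies and does not name humanized ones. A site applying the text as written has no named ground for excluding a subject who once had a non-anaphylactic reaction to a humanized antibody. A site applying the evident intention would exclude that subject.

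Two things are at stake. One is protection of the individual subject. The other is consistency of the population in which safety is described. Treatment-emergent adverse events are the primary variable (Protocol 12.4.1; SAP 2.5.1). SAP 2.7.1.2 lists hypersensitivity and serum sickness as adverse events of special interest. SAP 2.7.4.3 relates events of this kind to anti-drug antibody status. With one arm and no comparator, the reader of those tables depends on knowing who was eligible.

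**Working it through.** No arithmetic applies: the point rests on no figure, and the plan states none to reproduce. The check compares texts.

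**Step 1: the two statements side by side.**

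| Place | Content |
|---|---|
| Protocol summary and 5.2 criterion 2 | Related class defined as murine, chimeric or human antibodies |
| Protocol 1.1 | Ligelizumab is a humanized antibody |

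The word humanized does not appear in either copy of the criterion.

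**Step 2: is the list open or closed?** The criterion uses *i.e.*, which restates or defines. Where this protocol intends examples, it usually says so. Criteria 4 and 6 use *e.g.*, criterion 14 states that its list is not limiting, and so does criterion 17. Amendment 01 added non-limiting wording to the immunosuppressant row of Table 6-2, with the stated aim of showing that the row is not confined to the drugs named. Against that practice, the plain reading of criterion 2 is a closed list.

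**Step 3: does anything else name this history?** Take a subject with a past non-anaphylactic reaction to a humanized antibody other than ligelizumab.

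| Provision | What it reaches | Names this history? |
|---|---|---|
| Criterion 2, study-treatment limb | Reactions to the study treatments | No |
| Criterion 2, excipient limb | Reactions to an excipient of the study drug | Only if the reaction was to a shared excipient |
| Criterion 2, related-class limb | Three listed antibody types | Not on a literal reading |
| Criterion 7 | Earlier ligelizumab use | No |
| Criterion 14 | Rescue medications | No |
| Criterion 15 | Documented anaphylaxis | No, the reaction was not anaphylactic |
| Criterion 17 | Conditions judged to affect safety, interpretation or completion | No, general and discretionary |
| Table 6-2 | Prohibited medication and washout periods | No, it does not ask about past reactions |

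**Step 4: result.** On the literal text no criterion names the history. Exclusion then depends on how a site reads the related-class phrase, or on judgement under criterion 17. SAP 2.3 tabulates a baseline history of serum sickness, and no exclusion criterion names that history.

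Some text after criterion 24 in section 5.2 and one row of Table 6-2 are redacted, so Step 3 covers the legible provisions only.

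**The case against.** The strongest reply is that the operative words are the related class itself and that the parenthesis only illustrates it. To enrol such a subject, an investigator would have to hold that an antibody of ligelizumab's own type is unrelated to ligelizumab while murine and human antibodies are related. That defeats the obvious purpose. Many investigators would read the term human antibodies loosely, or use criterion 17, and exclude the subject anyway.

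Other provisions also lower the practical risk. Anaphylaxis of any cause is excluded. Subjects are observed for 2 hours after each of the first three doses, with readiness for anaphylaxis required (Protocol 6.7.2). Treatment must stop where continued participation might put the subject at risk (Protocol 9.1.1). Baseline histories of anaphylaxis, angioedema and serum sickness are tabulated, so part of the relevant background would be visible when events are interpreted.

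Much of this stands. It shows that the gap lies in the wording and may seldom decide a case. It does not remove the inconsistency, because the criterion then works only if each site reads past its definition, and observation after dosing is not an entry rule.

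Three stronger readings are tempting, and the documents do not support them:

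- **Previous omalizumab users as the route in.** Section 4.1 admits "Subjects treated with omalizumab previously as well as subjects with chronic spontaneous urticaria as their predominant disease", so a reader might infer that subjects with past reactions to a humanized antibody are expected. The documents never state omalizumab's antibody type, so this does not follow from them.
- **Inflated event rates.** A reader might infer that hypersensitivity rates would rise through selection, or count 1/65 per affected subject. The documents give no frequency of such histories, and 1/65 is the weight of any single subject in a study of about 65.
- **The related-class limb as the whole criterion.** Criterion 7 leaves the study-treatment limb little to do for ligelizumab, but the excipient limb is separate and remains in force.

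**Conclusion.** The inconsistency is real and verifiable from the text. The class definition in criterion 2, and its copy in the summary, omits the class that section 1.1 gives the study drug, and no other legible criterion names the resulting history. The consequence that can be claimed is that sites could decide the same history differently. It is not shown that such subjects would be enrolled, or that any event rate would change. The study is descriptive with no safety hypothesis, so no test is affected.

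The point rests on two assumptions: that *i.e.* is read in its ordinary defining sense, and that the redacted text contains no further hypersensitivity criterion. The omission itself is certain; its practical weight is modest and cannot be quantified from the documents. It still merits correction, because it sits in a safety eligibility rule of a trial whose primary purpose is safety.

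**What to change.** Reconcile the Key Exclusion criteria in the Protocol summary and criterion 2 in section 5.2 with section 1.1, so that the parenthetical list covers the class the protocol gives ligelizumab. Adding the word humanized to the list in both places would do this. Changing *i.e.* to *e.g.* as well would turn a defined list into an open one, which is a wider eligibility change and not needed to remove the inconsistency. Which histories should exclude a subject, and how broadly the class is drawn, is for the sponsor to confirm.

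The cost is a short text change at the next amendment, with the possible loss of a very few candidates. The change acts only on subjects not yet enrolled; Amendment 01 describes the study as still recruiting. It requires no change to the sample size or the SAP analyses.
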